4. SUBJECT ENROLLMENT

Study candidates will be primarily enrolled through social workers, medical assistants and nurses at MGH OB/GYN. After administering and scoring the EPDS, the social workers, medical assistants, and nurses will introduce the study and obtain permission from the study candidate to be contacted by study staff. We will also identify potential study candidates through their EPDS score in their medical records. We will then approach physicians of qualified candidates to obtain permission that their patient will participate in the study and permission that study staff contact candidate, if not approached through other OB staff. Physicians will not take part in the study recruitment. Candidates will secondarily be enrolled via study flyers and by study announcement in the hospital's websites.

5. STUDY PROCEDURES

5.1. Design.

Phase I: Screening (two stages).

First, study candidates (third trimester of pregnancy) will undergo screening via self-report questionnaire, the EPDS, to identify women at risk for PPD. Next, study candidates will be further screened over the telephone or in person at the OB by a study staff. For exclusion criteria, use of potentially confounding or interacting medications (e.g. antidiuretic hormone, steroids), and current mental disorders assessed by the mini Structural Clinical Interview for DSM (mini SCID). The treating obstetrician will be asked regarding contraindicating medical conditions (e.g., preeclampsia). Also, candidates' medical records will be reviewed for exclusion criteria. For those who will be enrolled from the Mothers Wellbeing Study, we will enroll them based on their PDI score obtained as part of the Mothers Wellbeing Study. Medical records will be reviewed for exclusion.

Phase II: Assessment. i) At *approximately 32 weeks of pregnancy*, study Sbj will complete additional self-report questionnaires and 40 mL of blood will be collected from Sbj, if she agrees. ii) *Postpartum (PP) Day 1*, Sbj will complete further self-report questionnaires. *Starting 8 hours after delivery with modification in the start time up to 12 hours postpartum if needed*, Sbj will self-administer the first dose of study medication in the hospital. In cases of delays due to medical procedures (e.g., emergency C-section) medication start time will be extended to up to 24 hours post-delivery. iii) *PP Days 1-4*, Sbj will continue to self-administer the medication in the hospital and then at home. iv) *Approximately PP Day 5*, Sbj will complete additional self-report questionnaires. v) *2 months, but with modification up to approximately 3 months PP*, Sbj will complete the same self-report measures and participate in a short video-clip with her infant. 40 mL of blood will be collected from Sbj, if she agrees. Following this, PI will answer any questions Sbj may have and make mental health treatment referral, if indicated and desired. Women enrolled through the Mothers Wellbeing Study will begin this study at PP Day 1.

5.1.1. Assessment # 1 (after approximately 32 weeks pregnancy). At MGH, Sbj will provide written informed consent after a full explanation of the procedures. Alternatively, for the convenience of the Sbj given their condition as well as to adhere to their visits to the OB, Sbj will be consented by the study physician over the phone in the presence of the PI or Research Fellow. If the consenting process occurs via telephone, the PI will first meet with the candidate and give her the written consent for her to review. She will then review the Consent Form with the study physician over the phone. The PI will be able to address any questions that may arise after the phone call. At this time, Sbj will be asked for her permission for study staff to contact her partner. Sbj will be provided with the "Partner Study Introduction Letter" to give to her partner, which invites the partner to participate in the study. Her decision on this matter will not affect her enrollment in the study. Next, study staff will email a copy of the consent form to the Sbj. The study doctor will sign the document upon receipt from Sbj. Next, study staff and the PI will administer assessment to Sbj via self-report questionnaires (60 minutes total) pertaining to demographics, medication usage (Medication Questionnaire [MED]), attachment (Maternal-Fetal Attachment Scale [MFAS]), mental health (Brief Symptom Inventory [BSI], PTSD CheckList for DSM-5 [PCL-5 1]), personality (Five Factory Inventory [NEO-FFI]), relationships and social support (Experiences in Close Relationships-Revised Questionnaire [ECR-R] and

Multidimensional Scale of Perceived Social Support [MSPSS]), trauma history (Life Events Checklist for DSM-5 [LEC-5], Childhood Trauma Questionnaire Short Form [CTQSF]), sleep (Bergen Insomnia Scale [BIS]), and expectations about delivery (Wijma Delivery Expectancy/Experience Questionnaire [W-DEQ 1]). All study questionnaires will be completed electronically, with the option to complete hard copies. If needed, self-report measures may be completed remotely. Following this, Sbj will be taught to self-administer the nasal spray containing either drug or placebo. Finally, if agreed by Sbj, 40 mL of blood will be collected from Sbj from venipuncture specimens performed for the purpose of this study and related studies. Samples will be later analyzed for hormone levels (e.g., oxytocin and cortisol) and DNA. Sbj (and her partner, if involved) will be contacted approximately 1 month after Assessment 1 as a reminder about her participation in the study.

5.1.2. Assessment # 2 and initial study medication administration (approximately 8 hours after delivery). Study staff will receive epic notification indicating that Sbj has been admitted to the Labor and Delivery Unit (L&D). Sbj will complete questionnaires (25 minutes total) at MGH's postpartum unit targeting mental health (BSI), peritraumatic responses (Peritraumatic Dissociative Experiences Questionnaire [PDEQ], Peritraumatic Distress Inventory [PDI], [W-DEQ 2]), depressive symptoms [EPDS], maternal bonding (Mother-to-Infant Bonding Scale [MIBS], and medication (MED). Additionally, as prescribed in the physicians order sheet (OXT order sheet), Sbj will self-administer the study medication (Syntocinon 40 mg/ml or placebo nasal spray, per randomization schedule), 1 spray into each nostril, before feeding their baby if possible, q 4 hours, including nighttime.

5.1.3. Continued study medication administration (up to 4 days after delivery). Sbj will continue using the spray as instructed over 4 consecutive days. Sbj will complete a diary recording their use of the study medication over the 4-day period (10 minutes total). Drug diary will be completed electronically, with the option to complete a hard copy version. Sbj will be called after the assessment #2 to provide any assistance with the study medication or the diary, and to monitor responses to questionnaires. Sbj will also be called or texted as a reminder to use the spray over the 4 days, if desired. Further, as part of routine hospital care, Sbjs' vital signs are taken in the postpartum unit before medication administration and are consistently monitored by the nurses during the course of the Sbjs' hospital stay as part of routine hospital care.

5.1.4. Assessment # 3 (approximately 5 days after delivery). Sbj will complete self-report questionnaires (30 minutes total) pertaining to mental health (EPDS, PCL-5 2, BSI, PTGI), breastfeeding (Index of Breastfeeding Status [IBS]), maternal bonding and attachment (MIBS, Postpartum Bonding Questionnaire [PBQ], Maternal Attachment Inventory [MAI]), childbirth experience (W-DEQ 2), and medication (MED). Sbj will be called after assessment to monitor responses to questionnaires. Additionally, if Sbj's partner expressed interest in participating in the study, they will receive the "Partner Recruitment Letter" and, upon implied consent, will complete the EPDS (EPDS-P) and MIBS (MIBS-P) adapted for partners. Partners will complete all questionnaires electronically, with the option to complete hard copies.

5.1.5. Assessment # 4 (approximately 2 months after delivery). Sbj will complete (40 minutes total) concerning mental health (EPDS, PCL-5 2, BSI), bonding (MIBS, PBQ), breastfeeding (IBS), child development and temperament (Ages and Stages Questionnaire, 2 months [ASQ-3],

Infant Behavior Questionnaire [IBQ-R]), psychological growth (PTGI) and medication (MED), administered by PI and study staff research assistants. If needed, self-report measures may be completed remotely. Sbj will also participate in a short video-clip of free play with their infant (10 minutes total) obtained by research staff (see Video Completion Form), which will later be coded using Coding Interactive Behavior (CIB). Sbj is instructed to freely interact with baby. Assessment may be completed at Sbjs home, if desired. Child development will also be measured by the Bayley Scales of Infant Development (Bayley-III), relevant for the age group studied. The Bayley-III, which focuses on observational behavior, will be conducted by PI or by trained research staff, supervised by PI. Finally, if agreed by Sbj, 40 mL of blood will be collected from Sbj from venipuncture specimens performed for the purpose of this study and related studies. Samples will be later analyzed for hormone levels (e.g., oxytocin and cortisol) and DNA. After completion, a member of the study team will answer any questions Sbj may have about the study and provide mental health referral, as needed and desired. Additionally, partner's enrolled in the study will complete the EPDS-P and MIBS-P.

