3. SUBJECT SELECTION

For Oxytocin study

3.1. Inclusion Criteria. 1) Third-trimester pregnant women being followed at the MGH Obstetrics Program who are at risk of PPD as indicated by their scoring >9 on a prenatal administration of the Edinburgh Postnatal Depression Scale (EPDS). (Note: Although the adjective “Postnatal” refers to the use of the EPDS during the *postpartum* period, this instrument is also used as a *prepartum* screening instrument for PPD risk.) Additionally, we will enroll women with score of >21 on the Peritraumatic Distress Inventory (PDI) who might also be at risk for bonding impairment from PPD and PP-PTSD.

3.2. Exclusion criteria. 1) Age <18 or >50; 2) Failure to participate in regular prenatal check-ups; 3) Current diagnosis of psychosis; 4) Obstetric complication (e.g., preeclampsia, excessive hemorrhaging, gestational diabetes insipidus, emergency Caesarian section resulting in the newborn being admitted to the NICU). Note that planned Caesarian section will not serve as an exclusion criterion because immediate contact with the newborn occurs after the procedure.); 5) Use of potentially confounding or interacting medications (e.g. antidiuretic hormone, steroids); 6) Complicating pediatric medical condition in the newborn.; 7) suicidality (candidates indicating 2+ on EPDS item 10 will be further assessed by PI, a licensed clinical psychologist); 8) current substance abuse.

3.3. Recruitment methods. 3596 women delivered a baby at Massachusetts General Hospital (MGH) in 2012. During proposed five-year project period, we plan to recruit 110 subjects (Sbj's) (who satisfy the inclusion and exclusion criteria) and expect a drop-out rate of 20% between assessments, resulting in an anticipated final sample of 56 women. Additionally, we plan to recruit and study 88 partners (starting at day 1 postpartum, taking into account women's drop-out rate between pre-partum and day 1 postpartum assessments), also expecting a drop-out rate of 20% between assessments, resulting in a final sample of 56 partners.

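### Women who enter from the Mothers Wellbeing Study have no scheduled PCL-5 or trauma history before dosing, so earlier PTSD symptoms may not be separable from childbirth-related ones in this route

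*Protocol*

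**What the plan says.** Protocol 3.1 admits women on a prenatal EPDS score and adds a second route: "we will enroll women with score of >21 on the Peritraumatic Distress Inventory (PDI". For women from the Mothers Wellbeing Study, 5.1 Phase I says "we will enroll them based on their PDI score obtained as part of the Mothers Wellbeing Study", with a check of medical records for exclusions. Phase II then says "Women enrolled through the Mothers Wellbeing Study will begin this study at PP Day 1".

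The PTSD-related instruments are placed as follows:

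- **Assessment 1 (5.1.1, late pregnancy):** "PTSD CheckList for DSM-5 [PCL-5 1" and trauma history (LEC-5, CTQSF).
- **Assessment 2 (5.1.2, first-dose visit):** "peritraumatic responses (Peritraumatic Dissociative Experiences Questionnaire [PDEQ], Peritraumatic Distress Inventory [PDI], [W-DEQ 2", together with BSI, EPDS, MIBS and MED. No PCL-5 and no trauma history.
- **Assessment 3 (5.1.4, Day 5):** "mental health (EPDS, PCL-5 2, BSI, PTGI".
- **Assessment 4 (5.1.5, two months):** PCL-5 2 again.

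The psychiatric exclusions in 3.2 are "Current diagnosis of psychosis", suicidality and current substance abuse. PTSD is not listed. Phase I, however, refers to "current mental disorders assessed by the mini Structural Clinical Interview for DSM (mini SCID" as part of screening for exclusion.

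Lower PP-PTSD symptoms at Day 5 and two months are part of the primary hypothesis (2.1). Protocol 6.1 names no baseline PTSD covariate. The SAP compares groups at each time point with unadjusted Mann-Whitney tests, after multiple imputation.

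**The concern.** Section 3.1 ties the PDI route to risk of bonding impairment from PPD and PP-PTSD, yet it is the route with no scheduled PTSD score before treatment. A woman with long-standing PTSD symptoms could enter on her PDI score, and nothing in the listed data would show that part of her later PCL-5 2 score was there before the birth.

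Three things are at stake. The first is precision, because a PTSD outcome that cannot be adjusted for its own baseline is estimated less sharply. The second is visibility: a chance difference between arms in earlier PTSD could be neither seen nor corrected among these women. The third is description. Protocol 6.3 counts learning how common posttraumatic stress is, how it runs and what predicts it as a successful result. Randomisation does not help there, because those statements depend on knowing which symptoms are new.

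The gap is specific to PTSD. EPDS and MIBS are both taken at Assessment 2, whichever way the woman entered.

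**Working it through.** **Step 1: trace the instruments by route.** The plan states no figure on this point, so the main check is a comparison of the visit schedules.

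| Item before the first dose | EPDS route | Mothers Wellbeing route |
|---|---|---|
| PCL-5 | Yes (Assessment 1) | Not scheduled |
| LEC-5, CTQSF | Yes (Assessment 1) | Not scheduled |
| Mini SCID | Described in Phase I | Not stated; record review only |
| PTSD named as an exclusion in 3.2 | No | No |
| EPDS, MIBS, BSI, PDI, PDEQ | Yes (Assessment 2) | Yes (Assessment 2) |

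Nothing in the Assessment 2 battery is presented as a measure of pre-birth PTSD. BSI is listed under general mental health, and PDI and PDEQ under reactions to the birth.

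**Step 2: outer bound on chance imbalance.** Inputs: 18 and 20 women (SAP), and a correlation r between pre-birth and later PCL-5 of 0.5 to 0.7 (assumed; not in the documents).

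- Standard error of a baseline difference between arms, in SD units: √(1/18 + 1/20) = 0.325.
- A one-SE imbalance moves the outcome difference by r × 0.325: 0.5 × 0.325 = 0.16 and 0.7 × 0.325 = 0.23 SD.

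This treats all 38 women as lacking a baseline, which is not the case: EPDS-route women are scheduled for PCL-5 1.

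**Step 3: scale to the route.** If a fraction f of women lack the baseline, with similar shares in each arm, the unseen part is √f × r × 0.325. The documents do not give f, so a range is shown.

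**Step 4: precision at stake.** With the baseline for everyone, the residual variance is proportional to 1 − r². With it for the EPDS route only, plus a route term, it averages 1 − (1 − f)r². Completing the baseline therefore cuts the SE of the treatment effect by 1 − √[(1 − r²) / (1 − (1 − f)r²)]. Example with f = 0.25 and r = 0.5: 1 − √(0.75 / 0.8125) = 0.039.

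| Assumed f | Unseen one-SE shift, r = 0.5 to 0.7 | SE cut from completing the baseline |
|---|---|---|
| 0.10 | 0.05 to 0.07 SD | 2% to 4% |
| 0.25 | 0.08 to 0.11 SD | 4% to 10% |
| 0.50 | 0.11 to 0.16 SD | 7% to 18% |
| 1.00 (outer bound) | 0.16 to 0.23 SD | 13% to 29% |

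For scale, the effect size planned in Protocol 6.2 is d = 0.32. The shifts are part of the sampling error that the unadjusted standard error already carries. Step 4 assumes that the late baseline correlates with the outcome as well as PCL-5 1 does. A retrospective score may do less well, so these gains are upper values.

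**The case against.** The strongest objections are these.

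- **A reader might infer that old PTSD is counted as childbirth PTSD.** The documents do not support that. They give no index event for PCL-5 2. The suffix is not a visit counter, since PCL-5 2 is used at both Day 5 and two months. W-DEQ 1 covers expectations of delivery and W-DEQ 2 the experience of it, so PCL-5 2 may likewise be a version tied to the birth. This is unproven, but it rules out the flat assertion.
- **A reader might infer that PTSD is settled as neither excluded nor measured.** The mini SCID text in Phase I points the other way, at least for third-trimester candidates. The parent study may also hold PTSD data, although only its PDI score is said to carry over. What stands is a conflict to reconcile and a gap in what is documented.
- **Treatment was randomised.** Earlier PTSD is balanced on average, and an unadjusted comparison is valid for a hypothesis about reducing symptoms. This stands in full. It does not rescue the prevalence, course and new-onset statements.
- **No woman need be dropped from an adjusted model.** Route is fixed before randomisation, so a missing-baseline term keeps everyone without biasing the treatment effect. The SAP also already uses multiple imputation. This stands, and the fix uses the route term. Imputing PCL-5 1 here would lean entirely on the other route's data.
- **A Day 1 PCL-5 follows the birth.** An ordinary one would pick up reactions to the delivery and is not interchangeable with PCL-5 1. This stands, and is why the wording of any added questionnaire matters.

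**Conclusion.** The gap is real and modest. As documented, women from the Mothers Wellbeing Study have no pre-dose PTSD score or trauma history. Unless PCL-5 2 is anchored to the birth, earlier and childbirth-related symptoms cannot be separated for them. The effect is on precision, on chance imbalance that stays hidden in this route, and on descriptive and new-onset statements about PP-PTSD.

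It is tempting to read the 0.16 to 0.23 SD in Step 2 as a bias in the treatment effect. It is not: it is ordinary chance variation, and it reaches that size only if every woman lacked a baseline. At an assumed quarter of women it falls to about 0.08 to 0.11 SD, and with few such women it is close to zero. The actual size cannot be fixed, because neither the number entering by this route nor the correlation is given. The case for acting is that the remedy is cheap, not that the randomised comparison is invalid.

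**What to change.** 1. **Obtain the baseline.** Transfer PCL-5 and trauma history from the Mothers Wellbeing Study if they were collected there. Otherwise add to Assessment 2 (5.1.2), before the first dose and for this route only, a PCL-5 explicitly worded for symptoms before the birth. LEC-5 and CTQSF can wait for a later visit.
2. **Use it in the analysis.** In the PTSD model under 6.1, adjust for pre-birth PCL-5 and include an entry-route (missing-baseline) term so that no woman is dropped. Carry this into the SAP.
3. **Limit the claims.** Report the number of women by route, and make no new-onset PP-PTSD statement for women whose pre-birth status is unknown.
4. **Clarify the text.** State the index event of PCL-5 2. Reconcile the mini SCID wording in 5.1 Phase I with the exclusion list in 3.2, and say whether that interview applies to this route.

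The SAP already reports a final sample of 38. For those women the workable parts are data transfer, the route term, reporting by route and the limits on claims; new collection before dosing applies only to any further enrolment.

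Cost: a data request, or a few extra minutes on the 25-minute Day 1 battery for this route. The remaining weakness is that a retrospective baseline, recalled after a distressing birth, is not identical to PCL-5 1.

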7. RISKS AND DISCOMFORTS

7.1. Study Medication. OXT nasal spray has been previously administered to women following childbirth. There are reports of mild side effects at a dosage to promote lactation for as early as day 1 postpartum (e.g., Fewtrell et al., 2006; Ruis et al., 1981). Mild complaints may include: breast and nipple discomfort (13-20 out of 100) and uterine cramps (5 out of 100). However, such side effects were also reported by women receiving placebo (Stern, 1961). As indicated in the drug brochure, women experiencing painful uterine cramps should not drive or operate machinery. Other uncommon side effects include bleeding from the nose after using the drug (1 out of 48) (Huntingford, 1961), unfamiliar sensation in the nose (5 out of 100), and complaint about taste (1 out of 100) (Stern, 1961). Use of the drug by participants who experience postpartum depression was reported to transiently lower mood (Mah et al., 2013). A subsequent study, however, by the same group did not mention these outcomes (Mah et al., 2015), nor were these outcomes reported elsewhere (Clarici et al., 2015). A recent study by Mah and colleagues (2017), based on the 2013 sample, reports no effect of IN-OXT on maternal sensitive interaction with own baby but more negative care giving response to another's baby. The authors warrant further research on IN-OXT in depressed mothers. Other potential undesirable effects mentioned in the nasal spray package insert but not encountered in the literature include: headache, nausea, rash and allergic dermatitis (all rare).

7.2. Questionnaires and video recording. Sbj may experience emotional distress from answering questions concerning their mental health and childbirth experience. Interacting with their infant on camera may cause Sbj discomfort.

7.3. Blood drawn. Sbj may experience discomfort from having blood drawn. Side effects may include bruising, swelling at the injection site, dizziness and lightheadedness.

7.4. Unknown Risks. There may be other risks and side effects that are not known at this time. If any significant new findings develop during the course of this study that may affect the risk: benefit ratio for participants, appropriate institutional reporting protocol will be followed.

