9. MONITORING AND QUALITY ASSURANCE

9.1. Administration of Protocol.

The protocol will be conducted in accordance with the protocol submitted to and approved by the Partners MGH IRB, as well as by NARSAD and ECOR. Sbjs will not be recruited until written notification of approval of the research project is issued by the IRB and NARSAD and ECOR are notified of the approval.

9.2. Data Monitoring. Given the reduced risk of this study, monitoring by the PI and Partners IRB should be sufficient. A physician investigator will review all laboratory/questionnaire results. The PI will closely monitor emotional dysregulation and concerning responses to questionnaire items that inquire about suicidality (BSI, question #9, responses of 2 or more; EPDS question #10, responses of “sometimes” or “yes, quite often”). Women who report suicidality in the screening and consent to the study will be monitored by the PI during their study participation. Likewise, the PI will monitor subjects who report suicidality in subsequent study assessments. If needed, the PI will conduct a suicidality assessment. Based on Sbj’s response, several actions will take place, including frequent contact with Sbj during study participation, suicide contract, referral for psychiatric consultation and treatment for medication,

if needed, and, in extreme cases, hospitalization. PI, who is a licensed clinical psychologist, will immediately evaluate subject suicide-related responses as data becomes available and will immediate attempt to contact subject for assessment and appropriate triage. The PI will review cases that are clinically significant and will notify the IRB in case of adverse events that may influence the IRB decision to continue or not the study trials, in accordance with IRB's policies. In the event possible serious or adverse effects of participation, [name]., an MGH psychiatrist who has served as a Medical Monitor on other studies conducted by the MGH PTSD group, and who is not an investigator on the present study, will be available to review the event and make recommendations to the PI and the IRB.

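### Section 7.1 cites a report of transient mood lowering on oxytocin, yet no mood or side-effect measure is scheduled between the start of dosing and about Day 5, so a brief dip may go undetected and cannot be compared by arm

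*Protocol*

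**What the plan says.** Protocol 7.1 lists the known effects of the spray. On mood it says: "Use of the drug by participants who experience postpartum depression was reported to transiently lower mood". It then qualifies this: a later study by the same group did not mention the effect, "nor were these outcomes reported elsewhere". It also gives breast and nipple discomfort (13-20 per 100) and uterine cramps (5 per 100), noting that women on placebo reported these too.

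Mood is measured at Assessment 2 (5.1.2, about 8 hours after delivery, with the first dose). The battery includes the BSI and "depressive symptoms [EPDS], maternal bonding (Mother-to-Infant Bonding Scale [MIBS], and medication (MED". The next measurement is Assessment 3 (5.1.4, about Day 5): "Sbj will complete self-report questionnaires (30 minutes total) pertaining to mental health (EPDS, PCL-5 2, BSI, PTGI".

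For the dosing days, 5.1.3 describes the diary ("Sbj will complete a diary recording their use of the study medication over the 4-day period (10 minutes total"), one call ("Sbj will be called after the assessment #2 to provide any assistance with the study medication or the diary, and to monitor responses to questionnaires") and optional reminders ("Sbj will also be called or texted as a reminder to use the spray over the 4 days, if desired"). It also mentions vital signs and nursing observation during the hospital stay as routine care.

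Protocol 9.2 states: "Given the reduced risk of this study, monitoring by the PI and Partners IRB should be sufficient". It adds that the PI will monitor emotional dysregulation and the suicidality items of the BSI and EPDS, and that a psychiatrist outside the study team can review possible adverse effects.

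**The concern.** The protocol names an effect that is short-lived and then places its mood scales at the two ends of the period in which that effect would occur. It also names common physical effects without saying how they will be elicited.

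Two things are at stake. The first is detection: a mild fall in mood that passes before Day 5 has no scheduled place to be recorded. The second is comparison. Since 7.1 says the physical effects also occur on placebo, only counts collected the same way in both arms are informative. Section 6.3 says the trial should inform a larger study and show whether the intervention is feasible. Tolerability during the dosing days is part of what the planners of that study would want to know.

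**Working it through.** The plan states no figure on this point, so the check compares timing and content. The arithmetic only sizes the window.

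1. **Daily dose, reproduced.** Protocol 2.1 gives 4 IU per nostril every 4 hours for four days. 24 h / 4 h = 6 administrations a day; 4 IU x 2 nostrils x 6 = 48 IU, matching the stated daily total.

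2. **Administrations in the window.** Four full days give 6 x 4 = 24. The heading of 5.1.3 instead sets the limit at four days after delivery, that is 96 h. The count is then (96 - start) / 4 + 1, with the start times allowed in 5.1:
   - start at 8 h: 88 / 4 + 1 = 23
   - start at 12 h: 84 / 4 + 1 = 22
   - start at 24 h: 72 / 4 + 1 = 19

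   The range is 19 to 24, counting the first dose.

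3. **What each contact is described as collecting.**

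| Contact | Timing | Described content | Mood or side-effect rating |
|---|---|---|---|
| Assessment 2 | about 8 h, first dose | EPDS, BSI, peritraumatic scales, MIBS, MED | mood only |
| Diary | four dosing days | medication use | none described |
| Call after Assessment 2 | not stated | help with spray or diary; questionnaire answers | none described |
| Reminders | dosing days, optional | spray use | none described |
| Nursing | hospital stay | vital signs, routine care | none described |
| PI monitoring (9.2) | not stated | emotional dysregulation; suicidality items | no instrument or contact named for the dosing days |
| Assessment 3 | about Day 5 | EPDS, BSI, PCL-5 and others | mood only |

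   Scheduled mood or side-effect ratings between Assessments 2 and 3: 0.

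4. **Side effects at any visit.** None of the instruments in 5.1.1 to 5.1.5 is described as asking about side effects; 5.1.1 labels MED as medication usage. For side effects, then, the gap is not confined to the dosing days.

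5. **Analysis.** Protocol 6.1 models psychometric scores. The SAP compares the groups on outcome measures at each time point. Neither describes a by-arm table of adverse effects.

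6. **Expected counts where a rate exists.** With the 18 women on oxytocin in the SAP:
   - breast and nipple discomfort: 18 x 0.13 = 2.3 to 18 x 0.20 = 3.6 women
   - uterine cramps: 18 x 0.05 = 0.9 women

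   These are the mild physical effects. The documents give no rate for mood lowering, so no expected count can be given for it, and no placebo rate for the physical effects.

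**The case against.** The protocol has weighed the mood signal and reports that it was not seen again. It also provides several routes by which a case could surface: the call after Assessment 2, nurses during the stay, the PI's monitoring, the outside medical monitor, and the EPDS and BSI at Day 5 followed by another call. The trial states no tolerability aim, and its main purpose is to estimate effect sizes.

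Much of this stands, and it rules out four stronger readings that a reader might infer.

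- **That the harm would be missed.** This does not follow. The routes above could each pick up a marked or lasting case. The documents also do not give the recall periods of the EPDS and BSI; if these look back over several days, the Day 5 scores may partly reflect an earlier dip.
- **That the diary records nothing but spray use.** The form is not in the documents. One sentence describes it, and that sentence neither excludes other items nor says how often entries are made.
- **That the trial enrols the group in which the effect was reported.** Section 7.1 reports it in women with postpartum depression. Section 3.1 enrols women at risk, by a prenatal EPDS above 9 or a PDI above 21. The groups are related but not the same.
- **That the trial would declare the drug well tolerated.** No such claim or aim appears.

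The objection does not close the gap. A study that does not mention an effect has not shown its absence. The calls, the nursing care and the PI's monitoring are described without a mood or side-effect question, and dosing continues at home after discharge. The medical monitor reviews events once they are known; nothing describes how they become known.

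**Conclusion.** The concern holds in limited form. As described, the plan has no systematic, scheduled capture of mood or side effects across about 19 to 24 administrations, and no listed instrument for side effects at any visit. A mild mood dip that resolves before Day 5 may go undetected. Neither it nor the physical effects in 7.1 can be compared by arm. The commitment in 9.2 to watch emotional dysregulation has no stated data source during dosing.

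This rests on two assumptions: that the unseen diary form matches its one-sentence description, and that MED covers what its label says. If either form already asks about mood or side effects, the point reduces to saying so in the protocol and tabulating the answers. The likelihood of a missed mood effect cannot be quantified, because the documents give no rate for it. The comparisons of bonding, depression and PTSD scores at the scheduled assessments are not affected.

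**What to change.** **Design.** In 5.1.3, add to the existing diary, once per day of dosing, one mood rating and a tick-list of the effects already named in 7.1. Route the entries to the PI review in 9.2, state in the protocol what the diary and the call after Assessment 2 ask, and add a by-arm table of both items to the analysis plan.

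**This trial.** The SAP, dated 12/27/2024, already reports a final sample of 38 (18 oxytocin, 20 placebo), so diary items can only serve a successor study. Here, tabulate by arm any events that were recorded, say plainly that mood and side effects were not systematically collected during dosing, and draw no tolerability conclusion for that period.

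**Cost.** About a minute a day for new mothers, some prompted minor complaints, a little more PI review time, and one table. The diary items would not capture the more negative response to another's baby that 7.1 also cites. No dose, action threshold or clinical rule is proposed.
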